8.5 Interim Disease Progression Monitoring

Based on the unpublished data from the New approaches to Brain Tumor Therapy Consortium, the median time of progression was 8.5 months among the newly diagnosed GBM treated by RT+TMZ (standard). The progression area outside radiation bed was about 20%. This study does not anticipate an above 30% progression rate in the spared NPC containing region. We expect a less than 30%, about 20% progression rate in the spared NPC containing region. However, we plan to monitory the progression rate throughout the trial. The progression rate in the spared NPC containing region will be monitored continuously throughout the cohort using the Bayesian stopping rule at patient numbers 10 and 20, after patients have a minimum of 6 months follow-up. We consider a 30% progression rate the highest limit that permits to continue this study and will stop early if there are excesses. The number of patients experiencing progression in the spared NPC containing region was assumed to follow a binomial distribution. Given the planned sample size of 30, a stopping boundary would be reached if the proportion of patients experiencing progression in the spared NPC containing region exceeds 30% with a posterior probability ≥ 0.6 . A recommendation for early stopping if 4 or more out of 10, or 7 or more out of 20 patients had disease progression in the spared NPC containing region. The probability of meeting the stopping boundary is 0.56 under a true probability of progression is 0.3.

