11.2 Data Safety Monitoring

All SAE's and major protocol deviations that occur at Johns Hopkins Hospital will be submitted to the IRB of record. Once in the IRB these reports of SAEs and major protocol deviations will be reviewed by the Sidney Kimmel Comprehensive Cancer Center Data Monitoring Committee (SMC) for review per Institutional guidelines. In addition, the overall study safety and potential activation of the study's early stopping rules will be assessed at the time of every SAE. The Data Safety Monitoring Committee with review this trial for safety annually.

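### The look schedule for the progression stopping rule is stated inconsistently in sections 8.5 and 11.2, and the quoted stopping probability of 0.56 does not match the two looks written

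*Combined protocol and SAP*

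**What the plan says.** Section 8.5 states that the progression rate in the spared region "will be monitored continuously throughout the cohort using the Bayesian stopping rule at patient numbers 10 and 20", and adds the condition "after patients have a minimum of 6 months follow-up". The boundary is reached when the proportion "exceeds 30% with a posterior probability ≥ 0.6". The counts that trigger a stopping recommendation are "4 or more out of 10, or 7 or more out of 20 patients had disease progression in the spared NPC containing region". No prior is given, and no count is listed for any other number of patients.

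The same section gives the sponsor's expectation: "We expect a less than 30%, about 20% progression rate in the spared NPC containing region". It reports one operating characteristic, a probability of 0.56 of meeting the boundary when the true rate is 0.3, and none at 20%.

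Section 11.2 says that "potential activation of the study's early stopping rules will be assessed at the time of every SAE". Section 8.5 contains the only stopping rule in the document, so section 11.2 can refer only to that one.

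**The concern.** The number and timing of looks determine how often a stopping rule fires when it should not. Three timings are on the page: continuous, at 10 and 20 patients, and at each SAE. The listed counts serve only two of these points, while the posterior criterion can be evaluated at any time. Suppose an SAE occurs with 14 evaluable patients. The committee then has a criterion, but no count, no prior, and no instruction on whether a look at that moment is valid.

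At stake is the chance that a 30-patient pilot running at its expected rate is recommended for early closure. The one published operating characteristic should settle which schedule was intended, but it does not correspond to the looks described.

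**Working it through.** **Inputs.** From section 8.5: binomial counts, boundaries of 4 out of 10 and 7 out of 20, posterior threshold 0.6 for a rate above 30%, planned size 30, expected rate about 20%, stated stopping probability 0.56 at a true rate of 0.3. Assumed here, because the plan is silent: the prior, and that every patient is evaluable at each look.

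**Step 1. Try to reproduce 0.56 with the two written looks.** Let X be the count in the first 10 patients and Y the count in the next 10.

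P(stop) = P(X ≥ 4) + Σ over k = 0 to 3 of P(X = k) × P(Y ≥ 7 − k)

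At a true rate of 0.3:
- P(X ≥ 4) = 0.3504
- second look: 0.0282×0.0106 + 0.1211×0.0473 + 0.2335×0.1503 + 0.2668×0.3504 = 0.1346
- total 0.3504 + 0.1346 = 0.485, not 0.56

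**Step 2. Find a schedule that does give 0.56.** With a Beta(1,1) prior the posterior probability that the rate exceeds 0.3, after x events in n patients, is the upper tail of Beta(1 + x, 1 + n − x):
- 3/10: 0.570, 4/10: 0.790
- 6/20: 0.551, 7/20: 0.723
- 9/30: 0.542, 10/30: 0.688

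This prior returns both listed counts and implies 10 out of 30 as the next one. A third look at 30 patients adds 0.0756 at a true rate of 0.3, so the total is 0.485 + 0.0756 = 0.561, which matches 0.56. The match is not unique: posterior checks after each patient from 10 to 20 under Beta(0.6,1.4), which also returns 4/10 and 7/20, give 0.557.

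**Step 3. Stopping probability at the expected 20% rate, listed counts.**
- Two looks: P(X ≥ 4) = 0.1209. The second look adds 0.1074×0.0009 + 0.2684×0.0064 + 0.3020×0.0328 + 0.2013×0.1209 = 0.0360. Total 0.157.
- Looks at 10, 20 and 30: a further 0.0154, total 0.172.
- Listed counts checked after every patient (4 within the first 10, 7 within the first 20): 0.157. Counts can only rise, so a boundary met early is still met at the scheduled look.

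**Step 4. Posterior criterion applied after every patient, true rate 20%.** The smallest stopping count was derived at each n up to 30, and the crossing probability found by exact recursion.

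| Prior | From the 10th patient | From the 1st patient |
|---|---|---|
| Beta(1,1) | 0.285 | 0.602 |
| Jeffreys, Beta(0.5,0.5) | 0.271 | 0.526 |
| Beta(0.6,1.4) | 0.235 | 0.501 |
| 814 beta priors that return 4/10 and 7/20 | 0.19 to 0.32 | 0.27 to 0.61 |

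From the 10th patient, the ratio to the two-look figure runs from 0.19/0.157 = 1.2 to 0.32/0.157 = 2.0. Every prior in the set gives more than 0.157, so the direction does not depend on the prior.

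**Step 5. SAE-time looks.** Not computable: the document gives no SAE rate, no SAE timing and no boundary specific to such a look.

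**The case against.** The strongest reply is that the passages can be read together without harm: progression is tracked throughout and judged only against the listed counts. On that reading the chance of stopping at 20% stays at 0.157, and a check prompted by an SAE costs nothing in false stops. Such a prompt can also be sensible, since under sections 9.1 and 10.1.1 a progression can itself qualify as an SAE, for example through hospitalisation. Crossing a count is also only a recommendation to stop. All of this stands, but the text does not say that this reading is the one meant, and it states a posterior criterion that permits others.

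A reader might infer that the rule would close most trials running at the expected rate, since 0.602 appears in the table. The documents do not support that. The figure needs an unstated Beta(1,1) prior, looks from the first patient, and boundaries the plan does not list. Under Beta(1,1) the probability of a rate above 30% is 1 − 0.3 = 0.70 before any patient is treated, already past the threshold, so that use can hardly have been intended. The six-month follow-up condition and the anchoring at 10 and 20 patients also point away from it.

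A reader might also infer that the rule should simply be declared to have two looks. That would leave in place a stated 0.56 which two looks do not deliver. The 0.56 itself favours a few discrete looks over continuous posterior checks from the first patient, which under Beta(1,1) would give 0.85 at a true rate of 0.3.

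**Conclusion.** The point holds as an inconsistency in a decision rule, with a moderate effect on its operating characteristics. The timing conflicts within section 8.5 and between sections 8.5 and 11.2.

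The 15.7% for the two written looks needs no prior. The increase to 23% to 28% (19% to 32% over the wider set) applies only if the posterior criterion is run after every patient from the 10th, and rests on assumed beta priors that return the listed counts. The range of 27% to 61% from the first patient is an extreme that depends on those assumptions, not a consequence of the plan.

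Separately, the reported 0.56 does not describe the two looks written. A third look at 30 patients probably explains it, but only the sponsor can confirm this. The point should be corrected, but it does not invalidate the design.

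**What to change.** Reconcile sections 8.5 and 11.2:

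- In 8.5, replace the wording about continuous monitoring with a list of the exact looks and the count at each, and state the prior.
- In 11.2, say that any SAE-time check uses only the boundaries listed in 8.5 and adds no new posterior look.
- Restate the stopping probability for the chosen looks at true rates of 0.3 and 0.2. For looks at 10 and 20 these are 0.485 and 0.157. For looks at 10, 20 and 30, with 10 out of 30 added, they are 0.561 and 0.172.

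The choice of looks is the sponsor's, and the quoted probability must match it. The cost is a few wording edits and one recalculation, with no extra patients or data. The stated operating characteristic may become less favourable: with two looks, the chance of stopping at a true rate of 0.3 falls from the quoted 0.56 to 0.485.

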TITLE: A Prospective Trial of Neural Progenitor Cell Sparing Radiation Therapy Plus Temozolomide for Newly Diagnosed Glioblastoma Multiforme

Research Site:	The Johns Hopkins University School of Medicine
Principal Investigator:	[name]., M.P.H. Department of Radiation Oncology [name] [contact] [contact] Email: [contact]
Co-Investigators:	[name]., Department of Radiation Oncology [name]., Department of Medical Oncology [name]., Department of Neuropsychology [name], N.P., Department of Oncology [name]., Department of Oncology [name]., Ph.D., Department of Oncology [name]., Department of Neurosurgery [name]., Department of Neurology [name]., Department of Psychiatry

Statistician:

[name]., M.S. [contact] Email: [contact]

Study Coordinators:

[name] [contact] [contact]

Research Nurses:

[name], R.N., B.S.N. [contact] [contact] [name] [contact] [contact]

[name], R.N.,

[contact]

[contact]

[contact] [contact]

> [name], R.N. [contact] [contact]

[name], B.S.

SCHEMA

Patient Eligibility: (See Section 3)

Newly diagnosed, histologically confirmed glioblastoma multiforme. Radiation and medical oncologist recommends adjuvant radiation plus temozolomide. Must begin therapy within 12 weeks of biopsy or surgery. No prior brain radiation. Age \geq 18 years. KPS > 60%. Signed informed consent.

Treatment Plan: (See Section 5)

Required sample size: 30 patients Anticipated accrual: 4-5 patients per month

TABLE OF CONTENTS

SC	HEM	P	age ii
ыc		•	11
1.	OBJE	CTIVES	1
	1.1	Primary Objectives	1
	1.2	Secondary Objectives	1
2.	BACH	KGROUND	1
	2.1	Study Disease and Rationale	1
	2.2	Temozolomide	3
	2.3	Correlative Studies Background	3
3.	PATI	ENT SELECTION	5
	3.1	Eligibility Criteria	5
	3.2	Exclusion Criteria	6
	3.3	Inclusion of Women and Minorities	6
4.	REGI	STRATION PROCEDURES	6
5.	TREA	ATMENT PLAN	7
	5.1	Surgery and Chemotherapy	7
	5.2	Radiation	7
	5.3	Duration of Follow Up	9
	5.4	Criteria for Removal from Study	9
6.	STUE	DY CALENDAR	10
7.	MAN	AGEMENT OF TOXICITY	11
	7.1	Acute Toxicity	11
	7.2	Late Toxicity	13
8.	STAT	ISTICAL CONSIDERATIONS	14
	8.1	Study Design/Endpoints	14
	8.2	Sample Size/Accrual Rate	15
	8.3	Stratification Factors	15
	8.4	Statistical Methods of Analysis	15
	8.5	Interim Disease Progression Monitoring	16
9.	ADVI	ERSE EVENTS AND REPORTING	17
	9.1	Definition of Adverse Event	17
	9.2	Radiation Related Adverse Event	17
	9.3	Chemotherapy Related Adverse Event	18

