8.2.2 Accrual

We anticipate enrollment of approximately 3-4 patients per month to the protocol with accrual completed in approximately 1-2 years.

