11. DATA AND SAFETY REPORTING/ REGULATORY CONSIDERATIONS

11.1 Data Quality Monitoring

In addition to the ongoing quality assurance evaluations for each individual at the time of treatment, there will be regular internal monitoring meetings between the principal investigator, a medical oncologist, and the study coordinator to assess the data quality. These meetings will occur annually and a monitoring report of the findings will be submitted to the Data Safety Monitoring Committee on an annual basis. Any protocol deviations or violations will be documented in the monitoring reports. The review will include: consent forms, eligibility criteria, protocol compliance, treatment administration, toxicity reports, response, regulatory compliance, case report forms (completeness as well as verifying that information coded on the case report forms are supported by source documents), and all other materials related to the trial. This is a Level I study under the SKCCC Data Monitoring Plan (6/26/2010). The Clinical Research Office QA group will assume external auditing responsibilities by performing an audit at the end of the first year and then periodically thereafter depending on the rate of accrual and prior audit results. The Safety Monitoring Committee will review this trial for safety and data quality annually.

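### At the stated monthly accrual rates, the two interim looks fall when 28 to 30 of 30 patients are already enrolled, so the early-stopping rule can spare at most about two enrolments

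*Combined protocol and SAP*

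**What the plan says.** Section 8.5 describes monitoring of progression in the spared region as continuous, but the operating rule is applied "using the Bayesian stopping rule at patient numbers 10 and 20, after patients have a minimum of 6 months follow-up". The criterion is that the proportion "experiencing progression in the spared NPC containing region exceeds 30% with a posterior probability" of at least 0.6. It is translated into two counts, both of events within that region: "A recommendation for early stopping if 4 or more out of 10, or 7 or more out of 20 patients had disease progression". The section does not say when the 6 months start or whether enrolment pauses meanwhile.

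Accrual is described in three ways. The Schema gives "Anticipated accrual: 4-5 patients per month". Section 8.2.2 gives a lower rate and a duration in one sentence: "We anticipate enrollment of approximately 3-4 patients per month to the protocol with accrual completed in approximately 1-2 years".

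Two other provisions bear on timing. Section 11.2 says that "potential activation of the study's early stopping rules will be assessed at the time of every SAE". Section 11.1 says: "The Safety Monitoring Committee will review this trial for safety and data quality annually".

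**The concern.** A rule meant to stop a trial early limits exposure only if patients remain to be enrolled when it is applied. Here the trial is small, the stated monthly accrual is fast, and each look waits for 6 months of follow-up. The wait is therefore about as long as the whole accrual period.

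The stake is specific to this trial. Section 2.1 accepts that sparing these niches could worsen tumour control, and Section 8.5 holds the only numerical stopping boundary in the protocol. If the looks come after enrolment has effectively ended, the rule can report an excess but does little to limit how many patients are exposed to it. A committee or ethics board reading Section 8.5 would expect more.

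**Working it through.** **Inputs.** N = 30 (Section 8.5, "Given the planned sample size of 30"). Looks at n = 10 and n = 20. Monthly rate r = 3-4 (Section 8.2.2) or 4-5 (Schema). Duration 1-2 years (Section 8.2.2). Radiation is 60 Gy at 2 Gy per fraction, five fractions a week (Section 5.2.1): 60/2 = 30 fractions, 30/5 = 6 weeks, about 1.4 months.

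**Lag from enrolment to maturity.** Section 8.5 does not define it, so I use two values: 6 months if counted from enrolment, and 6 + 1.4 = 7.4 months if counted from the end of radiation. The second is better supported, since Section 8.1.2 times the primary endpoint from radiation and the Section 6 calendar labels its follow-up visits as post-RT.

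**Step 1: the plan's own duration.** Duration = N/r. At 3-4 per month, 30/4 to 30/3 = 7.5 to 10 months. At 4-5 per month, 30/5 to 30/4 = 6 to 7.5 months. Neither gives 1-2 years. Working backwards, 1-2 years implies 30/24 to 30/12 = 1.25 to 2.5 per month.

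**Step 2: enrolment at each look.** Time of look = n/r + lag. Enrolled = min(30, n + r × lag), rounded down. For example, at 3 per month with lag 6, the first look is at 10/3 + 6 = 9.3 months, with 10 + 18 = 28 enrolled. In each cell the first value is for lag 6 and the second for lag 7.4.

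| Rate per month | Accrual ends (month) | Look 1 (month) | Enrolled at look 1 | Look 2 (month) | Enrolled at look 2 |
|---|---|---|---|---|---|
| 5 | 6.0 | 8.0; 9.4 | 30; 30 | 10.0; 11.4 | 30; 30 |
| 4 | 7.5 | 8.5; 9.9 | 30; 30 | 11.0; 12.4 | 30; 30 |
| 3 | 10.0 | 9.3; 10.7 | 28; 30 | 12.7; 14.1 | 30; 30 |
| 2.5 (1 year) | 12.0 | 10.0; 11.4 | 25; 28 | 14.0; 15.4 | 30; 30 |
| 1.25 (2 years) | 24.0 | 14.0; 15.4 | 17; 19 | 22.0; 23.4 | 27; 29 |

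All 30 are enrolled at look 1 once r reaches 20/6 = 3.3 per month (lag 6) or 20/7.4 = 2.7 per month (lag 7.4).

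**Step 3: patients not yet enrolled.** At 3-5 per month: 0 to 2 at look 1 and none at look 2. At one-year accrual: 5 or 2 at look 1 and none at look 2. At two-year accrual: 13 or 11 at look 1, and 3 or 1 at look 2.

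**Step 4: through radiation at look 1.** Taking radiation to start at enrolment, the number is r × (time − 1.4), rounded down and capped at 30. With lag 6 this is about 23 at 3 per month, 28 at 4 and 30 at 5. With lag 7.4 it is about 28 at 3 per month and 30 at 4 or 5.

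**Step 5: the stated probability of 0.56 at a true rate of 0.3.** An exact sequential binomial calculation on the two written looks gives 0.350 + 0.135 = 0.485. Adding a boundary of 10 or more of 30 contributes 0.076 and gives 0.561, which matches 0.56. Section 8.5 states neither that boundary nor the prior, but a uniform prior with the 0.6 criterion yields counts of 4, 7 and 10. On this reconstruction, part of the 0.56 arises at the full sample, where no enrolment can be prevented. This is a side observation; the timing result does not depend on it.

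**The case against.** **The accrual duration.** Section 8.2.2 also states 1-2 years, and at that pace the first look could spare up to 13 patients. This stands. A reader might infer from the monthly rates that the rule can protect no one; the documents do not support that, because one of their three accrual statements leaves it real value.

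**An unstated hold.** Two 6-month pauses added to 7.5-10 months give 19.5-22 months, which would fit 1-2 years. No passage says so. What stands is that the plan is silent on holds, not that it has decided against them.

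**Continuous monitoring and SAE checks.** Section 8.5 does speak of continuous monitoring, and Section 11.2 is wider than it may look: any SAE in any patient prompts a check of the stopping rules. A reader might also infer that a recurrence seen on MRI can never be an SAE. That goes too far, since Section 9.1 lists abnormal MRI findings among possible adverse events and Section 10.1.1 includes hospitalisation and important medical events. But a check needs a boundary to check against. Boundaries exist only for 10 and 20 patients with mature follow-up, and no passage names spared-region recurrence as a trigger.

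**Other protection.** Section 5.2.4 confines sparing to niche more than 2 cm from the PTV and requires tumour coverage to be kept, so Section 8.5 is not the only safeguard of any kind. It is the only numerical one.

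**The remedy may change little.** Section 8.5 cites a median time to progression of 8.5 months, and the first scheduled follow-up MRI is 6 months after radiation (Section 6). At 3-5 per month, four spared-region events among the first ten patients would seldom be seen before accrual closes. This largely stands: the gain from acting on the count is modest at those rates and larger at slower accrual.

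**Conclusion.** The concern holds for the monthly rates that the plan states. At 3-5 per month the first look can spare at most about 2 enrolments and the second none. It holds less strongly at the conflicting 1-2 year duration, where the first look leaves about 2-5 (one year) or 11-13 (two years) patients unenrolled and the second 0-3. The three accrual statements cannot all be right without something the plan does not say.

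The result assumes uniform accrual, radiation starting at enrolment and no pause. A delay before radiation starts, with follow-up counted from the end of radiation, would push the looks later still. If the annual review is counted from study opening, the first comes at month 12, after accrual has ended at 3-5 per month.

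A reader might also infer that everyone has been irradiated by the first look. That is not so at the low end: at 3 per month with follow-up counted from enrolment, about 23 patients have finished radiation.

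**What to change.** - **Section 8.5, trigger.** Count each recurrence classified as within the spared region when it is found. Treat the boundary as met as soon as the 4th event occurs among the first 10 patients or the 7th among the first 20, without waiting for the rest to reach 6 months. Later follow-up cannot undo a count already reached. State that each count closes when its look falls due; then only the timing changes, not the chance of reaching a boundary.
- **Section 11.2, reporting.** Make reaching that count a trigger in its own right, with immediate report to the Safety Monitoring Committee and suspension of enrolment pending its review.
- **Schema, 8.2.2 and 8.5, consistency.** Reconcile the three accrual statements, define when the 6 months start, and give the number expected to be enrolled at each look.
- **Section 8.5, description.** Say that without an enrolment hold, at 3-5 per month, the rule mainly flags harm and seldom limits exposure.
- **Optional.** If the sponsor wants the looks themselves to limit exposure, hold enrolment after patients 10 and 20. The cost is calendar time, at most about 6 to 7.4 months per hold under the lags used here, with no extra patients.

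Everything except the holds is a change of wording, plus the calendar time of any suspension triggered. Section 8.4 already refers to treated patients, so the trial is under way. If enrolment is complete, report the number enrolled at each look and correct the description of the rule.

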8.2 Sample Size/Accrual Rate

8.2.1 Sample Size

The required sample size is based upon the primary study hypothesis which is the rate of local recurrence within the spared NPC-containing region at 1 year post radiation therapy in patients treated with NPC sparing RT plus temozolomide for newly diagnosed GBM. Using conventional RT, approximately 20% of GBM recur outside of the tumor bed or radiation field margin (48). We hypothesize that there will be $\leq 25\%$ LR rate in the designated NPC avoidance region using our modified radiation technique, which is clinically acceptable. This is the first study to estimate the LR rate in the spared NPC containing region following NPC sparing RT for GBM. Given the clinically meaningful control LR rate in this region of 25% and a moderate variation among the patients, the 30 patients will have the optimal information gain (relative certainty) based on empirical information entropy to estimate the LR rate in the spared region (49).

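### Section 8.5 does not say what follow-up time its 30% stopping limit refers to, and its two listed looks give a stopping probability of 0.485 at a 30% rate, not the stated 0.56

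*Combined protocol and SAP*

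**What the plan says.** Section 8.5 sets the monitoring limit: "We consider a 30% progression rate the highest limit that permits to continue this study". The rule is applied "using the Bayesian stopping rule at patient numbers 10 and 20, after patients have a minimum of 6 months follow-up". The boundary is reached when the rate in the spared region "exceeds 30% with a posterior probability ≥ 0.6", which the plan turns into counts: "A recommendation for early stopping if 4 or more out of 10, or 7 or more out of 20 patients had disease progression" in that region. It then gives one operating characteristic: "The probability of meeting the stopping boundary is 0.56 under a true probability of progression is 0.3". The prior is not stated, nor is the start of the 6-month clock or any upper limit on follow-up at a look. The same section gives the plan's only timing figure, a median of 8.5 months to progression at any site under standard treatment, and expects a rate of about 20% in the spared region.

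The primary endpoint in section 8.1.2 is the site of recurrence 1 year after radiation. Section 8.2.1 hypothesizes at most a 25% "LR rate in the designated NPC avoidance region using our modified radiation technique, which is clinically acceptable". Section 8.4 judges the 25% by the lower bound of the exact 95% confidence interval. No section converts a rate seen at an interim look into a 1-year rate, or explains how the 30% relates to the 25%.

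**The concern.** Section 2.1 accepts that sparing these regions might worsen tumor control, and the interim rule is the plan's early safeguard against that. Anyone judging the safeguard has one number to go on, the 0.56. There are two reasons to doubt it. First, it should follow from the listed looks by exact binomial arithmetic, and it does not. Second, it is attached to a true progression probability with no time point. A reader who takes that as the 1-year rate, the scale of the primary endpoint, will credit the rule with more protection than it gives, because with a median of 8.5 months many first-year recurrences come after month 6 and would not yet be counted.

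**Working it through.** **Inputs.** Boundaries 4/10 and 7/20, limit 30%, posterior threshold 0.6, stated probability 0.56, minimum follow-up 6 months and median 8.5 months (section 8.5); 1-year endpoint (8.1.2); 25% (8.2.1); n = 30; accrual of 3-4 per month or over 1-2 years (8.2.2).

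**1. Reproducing 0.56.** Let X1 and X2 be the counts in the first and second ten patients, each Bin(10, p).

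P(stop) = P(X1 ≥ 4) + Σ P(X1 = k) · P(X2 ≥ 7 − k), for k = 0 to 3.

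At p = 0.30:
- Look at 10: 0.3504.
- Look at 20: 0.0282 × 0.0106 + 0.1211 × 0.0473 + 0.2335 × 0.1503 + 0.2668 × 0.3504 = 0.1346.
- Two looks together: 0.485.
- A third look at 30 with boundary 10/30 adds 0.0756, giving 0.561, which matches the stated 0.56.

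The count 10/30 is what the 0.6 rule would imply at 30 patients. With a uniform prior (an assumption, since none is stated), P(rate > 30%) is 0.790 at 4/10, 0.723 at 7/20 and 0.688 at 10/30, but 0.570, 0.551 and 0.542 with one event fewer. The other priors tried with mean 0.3 or 0.5 give the same three counts. So 0.56 very probably belongs to a three-look design that section 8.5 does not list.

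**2. Time scale, equal follow-up.** Assume spared-region recurrences follow exponential timing with the 8.5-month median: F(t) = 1 − 2^(−t/8.5). Then F(6) = 0.387, F(7.5) = 0.458, F(9) = 0.520 and F(12) = 0.624. The share of 1-year recurrences already seen is F(t)/F(12) = 0.620, 0.733 or 0.833. A 30% rate at the look therefore corresponds to a 1-year rate of 0.30/0.620 = 48%, 0.30/0.733 = 41% or 0.30/0.833 = 36%.

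Two-look stopping probability at p = (1-year rate × share):

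| 1-year rate | 6 months | 7.5 months | 9 months | Full 1-year outcomes |
|---|---|---|---|---|
| 25% | 0.07 | 0.12 | 0.18 | 0.31 |
| 30% | 0.12 | 0.21 | 0.31 | 0.485 |
| 35% | 0.20 | 0.33 | 0.45 | 0.66 |
| 40% | 0.30 | 0.46 | 0.60 | 0.80 |

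With the unlisted third look, the 30% row becomes 0.13, 0.24, 0.35 and 0.56. With a constant hazard in the spared region instead, a 1-year rate of 30% means 1 − √0.70 = 16.3% at 6 months, and the two looks stop with probability 0.08.

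**3. Time scale, staggered entry.** Six months is a minimum, so earlier patients contribute more. In a simulation, each look fell when the 10th or 20th patient reached 6 months, follow-up was capped at 12 months, and accrual was 3.5, 2.5 or 1.25 per month. At a 1-year rate of 30% the two looks stopped with probability 0.20, 0.26 and 0.36 (constant hazard) or 0.25, 0.30 and 0.38 (8.5-month curve). Across both curves the ranges were 0.10-0.23 at 25%, 0.33-0.55 at 35% and 0.49-0.71 at 40%.

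**The case against.** The strongest reply is that a stopping limit may deliberately sit above an estimation target, particularly in what section 8.4 calls a pilot, and that 0.56 was attached to a generic progression probability rather than a 1-year rate. Both points stand. The gap between 25% and 30% is not an error in itself, and on the scale observed at the look the only arithmetic shortfall is 0.56 against 0.485. Neither point supplies the missing time scale or makes the listed looks yield 0.56.

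The timing model is also open to challenge. The 8.5-month median is for progression anywhere, comes from unpublished data and has no stated origin. The spared region lies more than 2 cm from the planning volume and may behave differently. The sizes in the table are therefore illustrative. The direction is firmer: if recurrences occur between a look and month 12, the look understates the 1-year rate.

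Three stronger readings are tempting and should not be drawn:
- *That monitoring lets the trial run on at rates the plan calls unacceptable.* Section 8.2.1 calls rates up to 25% acceptable, but no section labels higher rates unacceptable. The final rule in section 8.4 excludes 25% only from 13/30 (43%, lower bound 25.5%); 12/30 gives 22.7%. As observed proportions, the interim boundaries (40% and 35%) are stricter than that.
- *That a clearly high 1-year rate would usually get past both looks.* At 40% with 9 months of follow-up the rule stops with probability 0.60, and staggered entry gives 0.49-0.71.
- *That the whole distance from 0.56 to 0.12-0.31 is due to follow-up.* The step from 0.56 to 0.485 comes from the unlisted third look; only the rest reflects immature data.

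**Conclusion.** The concern holds as a reporting and specification fault that should be corrected. The shortfall from 0.56 to 0.485 is exact arithmetic and needs no timing assumption. The further fall, if 30% is meant as the 1-year rate, is to about 0.12-0.31 with equal follow-up of 6 to 9 months, or 0.20-0.38 with staggered entry. The equal-follow-up figures assume exponential timing with the 8.5-month any-site median, the same timing in the spared region and the same clock as the endpoint. The staggered range also covers a constant hazard. All of them ignore death as a competing event. The documents do not settle whether the counts 4/10 and 7/20 are wrong for the sponsor's purpose, because they never say what rate, at what time, the rule is meant to catch.

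**What to change.** In section 8.5:
- State the follow-up time to which the 30% refers, when the 6-month clock starts, and whether later follow-up of earlier patients counts at each look.
- State the prior, and list every planned look. If there are two, replace 0.56 with 0.485, labelled as applying to a 30% rate on the scale observed at the look. If a look at 30 is intended, list it with its boundary.
- Add the stopping probabilities for 1-year rates such as 25%, 30%, 35% and 40%, with the timing assumptions and accrual rate written down.

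The sponsor should then reconcile sections 8.2.1, 8.4 and 8.5 and decide whether the counts still match its intent. All this costs wording and a short recalculation.

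Moving the stopping limit to 25% at 1 year would be a real design change and is not needed for the correction. With the same 0.6 rule, a uniform prior and 25% scaled by the shares above, the boundaries become 2/10 and 4/20 (6 or 7.5 months) or 3/10 and 5/20 (9 months). At the expected 20% 1-year rate the chance of stopping rises from 0.03, 0.06 or 0.09 to 0.41, 0.51 or 0.31. The sponsor should weigh that trade-off openly.
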